EPIDEMIOLOGY STUDY PROTOCOL

Concomitant Use of Dronedarone and Digoxin (or Statins) and the Risk of Digitalis Intoxication (or Rhabdomyolysis and Myopathy)

-- A Post-marketing Cohort Study Using the US LabRx Database

Dronedarone (SR33589)

Investigators/Authors: GPE Pharcoepidemiology, sanofi-aventis

Report type: Version 3.0 (final)

This study will be conducted in accordance with sanofi-aventis standard operating procedures for epidemiologic studies

Date: August 31, 2010

STUDY SYNOPSIS

Drug name: Dronedarone (MULTAQ®)

Title: Concomitant use of dronedarone and digoxin (or statins) and the risk of digitalis intoxication (or rhabdomyolysis and myopathy)-- a post-marketing cohort study using the US LabRx database

Background: This study is part of pharmacovigilance action to further evaluate dronedarone's potential interactions with digoxin and statins.

Objective(s): To evaluate the possibility of dronedarone increasing the dose-related adverse events of the following concomitantly used drugs: digoxin (digitalis intoxication) and statins (rhabdomyolysis and myopathy).

Study design: Retrospective cohort study

Study Population: The study population will be patients aged 18 years and older with a diagnosis of atrial fibrillation (AF) or flutter (AFL) who filled a prescription of digoxin (or statins) since the launch of dronedarone in the US, identified from the LabRx® database. Cohort entry date will be defined as the date of the first prescription of digoxin (or statins) dispensed after July 21, 2009, the launch date of dronedarone in the US.

Excluded from the cohort will be patients with the following conditions at cohort entry date: 1) less than six months of enrolment period; 2) a diagnosis of the outcome of interest within the last six months. Separate cohort will be identified according to each clinical outcome of interest.

Exposure measurement:

Exposure will be defined as on-drug treatment or off-drug treatment and categorized into the following three groups: 1) concomitant use of digoxin (statins) and dronedarone, 2) concomitant use of digoxin and amiodarone, and 3) digoxin (or statins) alone as the reference group, i.e. digoxin (or statins) without concomitant use of either dronedarone or amiodarone. The concomitant use of digoxin (or statins) and dronedarone (or amiodarone) will be defined as the treatment period during which a patient is on both of the drugs. Digoxin (statins) alone will be defined as the treatment period during which a patient is on digoxin (statins), but not on dronedarone or amiodarone. The treatment duration on digoxin (or statins) alone will begin accumulating on the first day of digoxin (or statins) prescription and continue with the subsequent continuous digoxin (or statins) prescriptions until: 1) a prescription for dronedarone overlapping the digoxin (or statins) days supplied, or 2) the end of the digoxin (or statins) days supplied (in addition to a grace period of up to 30 days, to account for non-adherence), 3) the occurrence of the outcome, 4) the enrollment end of membership, 5) the end of the observation period, whichever comes first. Likewise, the treatment duration of the concomitant use of digoxin (or statins) and dronedarone (or amiodarone) will begin on the first day of overlapping days supplied for digoxin (or statins) and dronedarone (or amiodarone) and will finish with the end of overlap of the days supplied for digoxin (or statins) and dronedarone (or amiodarone) (in addition to a grace period of up to 30 days) or the other endpoints, whichever comes first. The average daily dose of digoxin (or statins) will be adjusted for in the analysis. If a statistically significant association of interaction is observed, further analysis will be performed to check dose-response relationship.

Outcome(s) of interest:

Digitalis intoxication and rhabdomyolysis /myopathy are the outcomes of interest which will be analyzed separately. Digitalis intoxication will be defined as patients with the International Classification of Diseases, Ninth Revision, Clinical Modification (ICD-9) codes 972.1 or E942.1. A secondary analysis will be conducted among the patients who had a claim of the above ICD-9 codes plus at least one laboratory testing claim and/or hospitalization within 30 days.

Rhabdomyolysis and myopathy will be defined by an algorithm based on the ICD-9 codes, lab testing, and/or hospitalization that have been validated in a published study.

Covariates: Covariates in the multivariate analyses will include age at baseline, gender, cohort entry date, duration of AF/AFL, congestive heart failure (CHF), diabetes, hypertension, stroke, myocardial infarction, and dose of digoxin (or statins). The major medications that are known to have potent interactions with digoxin or statins will additionally be adjusted as potential confounders, while for rhabdomyolysis and myopathy, chronic renal failure will also be adjusted for.

Statistical analysis: Descriptive statistical analysis will be conducted to characterize the study participants. Cox proportional hazards regression modeling will be used to provide estimates of the relative hazard of the outcome of interest associated with concomitant use of digoxin (statins) and dronedarone, concomitant use of digoxin (or statins) and amiodarone, using digoxin (statins) alone as the reference group. Dose-response relationship with cumulative dose and treatment duration will be estimated if a positive association is observed.

Timelines: The interim study reports will be submitted annually in December, 2010 to 2014. The final study report will be submitted in December 2016 at the latest. The study observation period will be from July 20, 2009 (the launch date of dronedarone in the US to the latest date of available data by August 31 of each year in the yearly study report).

TABLE OF CONTENTS

LIST OF TABLES	6
LIST OF FIGURES	6
ABBREVIATIONS	7
1 INTRODUCTION	8
2 STUDY OBJECTIVE(S)	8
3 METHODS	8
3.1 STUDY DESIGN	8
3.1.1 Source population(s)/database(s) used	9
3.2 STUDY POPULATION.....	9
3.3 EXPOSURE MEASUREMENT	9
3.4 OUTCOME(S) OF INTEREST	11
3.5 COVARIATE(S).....	11
3.6 SAMPLE SIZE.....	12
3.7 STATISTICAL ANALYSIS.....	12
4 CONFIDENTIALITY AND ETHICAL CONSIDERATIONS	12
5 STUDY TIMELINES	12
6 REFERENCES	13
7 TABLES AND FIGURES	14
8 APPENDICES	17

LIST OF TABLES

Table 1 Distribution of gender, age, and region of patients in the LabRx as of 2008 and in the US general population in 2005	14
Table 2 Age distribution in AF/AFL Patients in the LabRx (1/1985-3/2008).....	15
Table 3 Estimated sample size	16

LIST OF FIGURES

N/A

ABBREVIATIONS

AF	Atrial fibrillation
AFL	Atrial flutter
CHF	Congestive heart failure
CPT	Current Procedural Terminology
GCP	Good Clinical Practice
GPE	Global Pharmacovigilance & Epidemiology
ICD-9	International Classification of Diseases, Ninth Revision
ICH	International Conference on Harmonization
ILD	Interstitial lung disease
NDC	National drug code
OR	Odds ratio
RMP	Risk Management Plan

1 INTRODUCTION

Dronedarone (MULTAQ[®]), like amiodarone, is a multi-channel blocker displaying antiarrhythmic properties of all four Vaughan-William's classes. Although structurally related to amiodarone, dronedarone shows different relative effects on individual ion channels, and its structure was modified with the intent to eliminate the non-cardiovascular effects of amiodarone. Dronedarone has been shown to be effective for reduction of the risk of cardiovascular hospitalization or death in patients with AF/AFL at the dose of 400 mg BID. The efficacy and safety of dronedarone have been evaluated in a comprehensive non-clinical testing program and extensive comprehensive clinical program in compliance with the International Conference on Harmonization (ICH) Good Clinical practice (GCP) guidelines.

The continuous assessment of all potential risks of dronedarone during its development has identified risk of drug-drug interactions with potent CYP3A4 inhibitors (such as ketoconazole). Dronedarone may have potential interactions with CYP3A4 substrates (such as some statins), and digitalis (such as digoxin). Although managed appropriately during clinical trials, the potential risks of these interactions need to be monitored in dronedarone users in the real life setting.

In order to further identify and evaluate dronedarone's potential interactions with frequently co-prescribed drugs, sanofi-aventis proposes epidemiologic studies using automated databases as part of the Risk Management Plan. They are done in addition to routine pharmacovigilance practices to ensure that the identified and potential risks are minimized in the real life setting, both in the US and in Europe. Using a US automatic claims database, LabRx, this epidemiologic study will be conducted once the number of dronedarone users is large enough to allow for analyses with sufficient statistical power.

2 STUDY OBJECTIVE(S)

The goal of this study is to provide safety information about dronedarone use in the US. The objectives of this study are to evaluate the possibility of dronedarone increasing the dose-related adverse events of the following concomitantly used drugs: digoxin (digitalis intoxication) and statins (rhabdomyolysis and myopathy).

3 METHODS

3.1 STUDY DESIGN

A retrospective cohort study is designed using information from a US claims database which will allow more facile implementation and explanation of the results among cohort of digoxin (statins) users and digoxin (statins) plus dronedarone users than a case-control study.

3.1.1 Source population(s)/database(s) used

The data source will be LabRx[®] (United HealthCare), an integrated medical and prescription-claims database augmented with laboratory data and linked to medical records and the National Death Index. As of January 2008, LabRx[®] consisted of seven-year data (since May 2000) and about 44 million unique members from 50 US states. This provides over 15 million covered lives (active patients) per year. If necessary, patients can be contacted to collect more information. About 30 million members' records (69%) contain at least one medical claim, about 27 million of them (61%) contain at least one prescription claim, and about 8 million records (19%) have at least one lab result (data provided by i3 Pharma Informatics on January 28, 2008 <http://www.i3global.com/Businesses/i3PharmaInformatics/>).

In general, LabRx database is representative of the US general population in terms of age, gender and region distributions (see Table 1). Since LabRx is an employment-based private insurance claims database, it has a lower proportion of patients aged 65+ years (6% in the LabRx vs. 12% in the US population). However, because of its large size, the number of subgroups in the database is large enough to allow for the studies with sufficient power. Our preliminary analysis identified 253,511 AF/AFL patients from January 1985 through March 2008 in the LabRx database, among which 127,516 patients (50.3%) were 65+ years old (see Table 2)

3.2 STUDY POPULATION

Separate study cohort will be identified according to the study objectives and the outcome of interest. To evaluate potential interaction of dronedarone and digoxin, patients aged 18 years and older with a diagnosis of AF/AFL (International Classification of Diseases, Ninth Revision, Clinical Modification (ICD-9) codes: 427.3X) who filled a prescription of digoxin since the launch of dronedarone in the US, will be identified from the LabRx[®] database. Likewise, to evaluate potential interaction of dronedarone and statins, we will identify patients aged 18 years and older with a diagnosis of AF/AFL who filled a prescription of statins since the launch of dronedarone. Cohort entry date will be defined as the date of the first prescription of digoxin (or statins) dispensed after July 21, 2009, the launch date of dronedarone in the US. The study observation period will be from July 21, 2009 to the latest date of available data by August 31 of each year in the yearly study report. Excluded from the cohort will be patients with the following conditions at cohort entry date: 1) less than six months of enrolment period in the managed care organization (UnitedHealthCare); 2) a diagnosis of the outcome of interest (prevalent cases) within the last six months.

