The treatment duration or follow-up time on digoxin (or statins) alone will begin accumulating on the first day of digoxin (or statins) prescription and continue with the subsequent continuous digoxin (or statins) prescriptions until: 1) a prescription for dronedarone (or amiodarone) overlapping the digoxin (or statins) days supplied, or 2) the end of the digoxin (or statins) days supplied (in addition to a grace period of up to 30 days, to account for non-adherence), 3) the occurrence of the outcome, 4) the enrollment end of membership, 5) the end of the observation period, whichever comes first. The follow-up time of the concomitant use of digoxin (or statins) and dronedarone (or amiodarone) will be defined using the same methodology as described above. It will however begin on the first day of overlapping days supplied for digoxin (or statins) and dronedarone (or amiodarone) and will finish with the end of overlap of the days supplied for digoxin (or statins) and dronedarone (or amiodarone) (in addition to a grace period of up to 30 days) or the other endpoints, whichever comes first. Prescriptions will be treated as continuous if they are not interrupted by a break of greater than 30 days. If a gap of greater than 30 days occurred, patients may still contribute follow-up time (defined as a separate treatment episode) to digoxin (or statins) alone or the concomitant medications as appropriate, until they are right-censored at the first occurrence of: 1) the outcome, 2) the enrollment end of membership, and 3) the end of the observation period.

Given that digoxin (or statins) may be administered at a lower dose when used in combination with dronedarone than the use of digoxin (or statins) alone, and the drug interaction effect may be dose-related, the average daily dose of digoxin (or statins) will be adjusted for as a covariate in the analysis. It will be calculated as the total quantity prescribed divided by the total days supplied. If a statistically significant association of interaction is observed, further analysis will be performed to check dose-response relationship. For statins, the analyses will be conducted at equally effective doses which will address the effect of dose with the same cholesterol lowering effect. Based on published literature comparing statins efficacy, the following equally effective doses will be used in the secondary analysis for statins: atorvastatin 10mg, simvastatin 20mg, lovastatin 40mg, and pravastatin 40mg¹⁻².

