5 STUDY TIMELINES

The interim study reports will be submitted annually in December, 2010 to 2014. The final study report will be submitted in December 2016 at the latest. It is estimated that the LabRx database may not provide sufficient statistical power until 2014 for any event of interest to rule out a

hazard ratio of 1.5. However, the sponsor will check the number of incident of digitalis intoxication and rhabdomyolysis /myopathy, the number of potential study participants, patients who received prescriptions of dronedarone and digoxin (or statins), and statistical power based on the above identified number of events and dronedarone users each year. Provided that 336 or more events are captured for any outcome(s) of interest before 2014 which will be sufficient to rule out at least a hazard ratio of 1.5, the final data analysis and study report for the particular outcome(s) will be initiated immediately.

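### Six months' enrolment is tested only once, at the first fill after launch, so members who qualify later are never admitted and precision is lost

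*Protocol*

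**What the plan says.** Protocol Section 3.2 gives each patient a single entry date: "Cohort entry date will be defined as the date of the first prescription of digoxin (or statins) dispensed after July 21, 2009". The exclusions are tied to that date and remove the patient, not the fill: "Excluded from the cohort will be patients with the following conditions at cohort entry date". The first exclusion is "less than six months of enrolment period in the managed care organization (UnitedHealthCare"); the second is a diagnosis of the outcome in the preceding six months. The Study Population paragraph of the synopsis sets the same test: "Excluded from the cohort will be patients with the following conditions at cohort entry date: 1) less than six months of enrolment period".

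The only wording that lets time resume later is in Section 3.3: "If a gap of greater than 30 days occurred, patients may still contribute follow-up time (defined as a separate treatment episode"). It concerns breaks in drug supply among patients already in the cohort. It does not re-test enrolment.

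Section 5 gives the setting, in a sentence whose target is a hazard ratio of 1.5: "It is estimated that the LabRx database may not provide sufficient statistical power until 2014 for any event of interest to rule out a".

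**The concern.** Take a member who joins in January 2010 already on digoxin. The first fill in the plan comes within weeks, so enrolment on that date is far short of six months and the patient is excluded. The exclusion stands even if the patient stays covered for years and later starts dronedarone. A member who joined in March 2009 and filled in August 2009 is lost in the same way, as is anyone who first starts the drug within six months of joining.

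Entry at the first fill would be natural in a new-user study. Here Sections 3.2 and 3.3 require no drug-free period, so an established user is admitted if enrolled long enough. The six months serve as look-back for prior outcomes (Section 3.2) and for baseline history (Section 3.5), and a later fill with six months of enrolment behind it supplies the same look-back. The rule therefore discards usable reference and co-exposed time. At stake are the width of the intervals and how soon the 336-event trigger in Section 5 is reached. The retained cohort is also weighted to longer-tenured members.

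**Working it through.** **1. The protocol's own event target.** Inputs: two-sided alpha 0.05, 80% power, dronedarone prevalence 17.1% (Section 3.6, Table 3), hazard ratio 1.5 (Section 5). Events = (1.960 + 0.842)² / [0.171 × 0.829 × (ln 1.5)²] = 336.8, against 336 stated. The target is reproduced to within rounding.

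**2. The stated detectable hazard ratios.** HR = exp[(1.960 + 0.842) / √(events × 0.171 × 0.829)].

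- Digoxin, 5 years: 44,000 × 1.1% = 484 events gives 1.40, against 1.42 stated.
- Statins, 5 years: 86,000 × 0.3% = 258 events gives 1.59, against 1.61 stated.

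This is close but not exact, and it makes no reduction for the 30% censoring given under Table 3. The steps below therefore scale the stated hazard ratios and do not replace them.

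**3. If the projected cohort sizes ignored the rule.** Let f be the share of users lost. The protocol gives no f, so 10%, 20% and 30% are assumptions. If the lost users resemble the retained ones in event rate, follow-up and dronedarone use, ln(HR) grows by 1/√(1 − f).

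| f | Digoxin N | Digoxin HR (stated 1.42) | Statin N | Statin HR (stated 1.61) |
|---|---|---|---|---|
| 10% | 39,600 | 1.45 | 77,400 | 1.65 |
| 20% | 35,200 | 1.48 | 68,800 | 1.70 |
| 30% | 30,800 | 1.52 | 60,200 | 1.77 |

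Example: ln 1.42 = 0.351; 0.351/√0.8 = 0.392; exp(0.392) = 1.48.

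Digoxin reaches 1.5 when 1 − f = (ln 1.42 / ln 1.5)² = (0.351/0.405)² ≈ 0.75, that is, at a loss of about 25%. The statin figure is above 1.5 before any loss.

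**4. If the projections already applied the rule.** Nothing is lost against plan, and later entry would be a gain. ln(HR) shrinks by √(1 − f), giving about 1.40, 1.37 or 1.34 (digoxin) and 1.57, 1.53 or 1.49 (statins). These are best cases, because later entrants have less follow-up and some of their co-exposed time would be set aside (see the fix).

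**5. Could joiners be a non-trivial group?** Section 3.1.1 reports "about 44 million unique members from 50 US states. This provides over 15 million covered lives (active patients) per year". If 15 million is a stable stock, (44 − 15) million over roughly 7 years is about 4.1 million joiners a year, or 28% of the stock. Counting May 2000 to January 2008 as 7.67 years gives 3.8 million, or 25%. This covers members of all ages. It shows only that joiners may matter and does not give f.

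**The case against.** The strongest objection is that simple delayed entry is not free of bias. Dronedarone was not marketed before launch, and a retained patient who enters well after launch has at least six enrolled months without a fill of the index drug. The start of dronedarone co-exposure is therefore essentially always observed under the present rule. Delayed entry would admit members who joined on both drugs, or began co-use in their first six months. They would enter part-way through co-exposure, and only if free of the outcome until then. Early interaction events would be missing and survivors would supply the co-exposed time, which can pull the hazard ratio toward 1 in a safety study. This stands as an objection to unrestricted delayed entry. A limit on which co-exposed time counts answers it.

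The second objection is about size. A reader might infer from the membership counts that a quarter of the study population turns over each year and that a large, calculable share of user time is lost. The protocol does not support this. It does not describe turnover. The 25% to 28% is an inference for all members, of whom 6% are 65 or older (Table 1), against about half of AF/AFL patients (Table 2). The protocol also does not say what share of users join already on the drug. This objection stands in full.

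Third, Section 3.6 does not say whether the 44,000 and 86,000 already apply the enrolment test, and Section 5 provides for yearly checks of events, users and power. A reader might conclude that the rule makes the study miss its planned power. That is not established, and a shortfall would probably be noticed. The yearly check would not recover the excluded patients.

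**Conclusion.** The point holds as one of efficiency. As written, the protocol tests enrolment once per patient and has no route back. That the exclusion is permanent is an inference from the single entry date and the absence of a re-entry rule, but no other reading fits the text. The design admits established users and so has no need of the restriction.

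The consequence is lost precision and a cohort weighted to longer-tenured members. A reader might go further and suspect bias between the dronedarone and reference groups, but nothing in the protocol shows it: the rule applies whatever the antiarrhythmic exposure.

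The size is unknown. Over an assumed 10% to 30% loss, with projections that ignored the rule, the 5-year detectable hazard ratio rises to 1.45–1.52 for digoxin and 1.65–1.77 for statins. If the projections applied the rule, the stated figures stand and could be improved. This is a worthwhile, inexpensive change, and it does not threaten the study's validity.

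**What to change.** In Section 3.2 and the synopsis, define cohort entry as the first digoxin (or statin) fill after launch on which all criteria are met: six months of prior enrolment and no outcome in those six months. Start the baseline look-back and follow-up from that fill, and count no earlier time.

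For patients admitted this way, count dronedarone or amiodarone co-exposed time in the main analysis only for overlaps that begin on or after entry. Use overlaps already under way at entry only in a sensitivity analysis.

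State in Section 3.6 whether the projected cohort sizes apply the enrolment test.

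The cost is a few sentences and slightly more cohort programming on the same claims data. Some left-truncated co-exposed time is set aside to avoid depletion of susceptibles, so not all of the recovered time reaches the main analysis.
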